3.4.2.4.3. HS-RDT/RDT test positivity during RACD intervention

Test positivity by HS-RDT and RDT will be monitored throughout the intervention period. There is no formal sample size calculation for this outcome, but based upon an estimated 720 cases in Lao PDR over the study period, an average of 5 households per response event, 4 people per household, and 4 forest-workers per case, we estimate a total of 17,280 individuals will participate in testing during RACD in Laos.

3.4.2.5. Data collection

3.4.2.5.1. Confirmed malaria case incidence

The confirmed parasite incidence from all reporting units (including HCs, district hospitals, VMWs with RDTs, and PPM sites) will be captured throughout the study with support from study or health center staff. In the months prior to the start of study activities, all villages within each health facility catchment area will be mapped, and trainings conducted with health facility staff to systematize the collection of village names at health facilities for confirmed malaria cases. Routine supervision of health facility staff will be conducted by study staff to ensure accurate recording of village names in health facility registers throughout the trial. Forest sites visited by malaria cases will be recorded and mapped where possible.

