Research objectives	
Primary Objective: To evaluate the effectiveness of reactive case detection (RACD) using HS-RDTs, targeting both village and forest working populations, compared to control for reducing the health center catchment-level incidence and prevalence of P. falciparum and P. vivax within two provinces in Lao PDR.
 
Secondary Objectives:
 
 1. To determine the operational feasibility, cost-effectiveness, and acceptability of targeting high-risk populations with community-based reactive case detection strategies aimed at reducing P. falciparum and P. vivax transmission among village and forest working populations. 2. To determine the operational feasibility and safety of conducting G6PD testing and PQ administration and follow-up at the community level. 3. To determine factors associated with G6PD testing after referral to district or provincial-level facilities for persons with P. vivax positive RDT results, and subsequent adherence to Primaquine treatment. 4. To assess malaria vector species composition and bionomics in both village and forest settings
Study site and target populations	Total population of approximately 120,000 in 32 health center catchment areas of two Provinces in Lao PDR (Champasak and Saravan Province)
Study design	A cluster randomized controlled trial design will be used to evaluate the enhanced RACD intervention against standard of care
Primary outcome measures for assessing impact	
 1. Cumulative incidence over the study period at the health facility level 2. Prevalence of infection (P. falciparum and/or P. vivax) using qPCR 3. HS-RDT and RDT test positivity rate for RACD
Data collection and sampling period	18 months from start date (June 2019 – November 2020)

Sample size	32 health center catchment areas in Lao PDR

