2.5. Study overview

To test this hypothesis, this study will employ a cluster randomized controlled trial design with two comparison arms:

1. **Control:** standard of care - passive case management provided through community-based VMWs and existing health facilities; includes village-based RACD with conventional RDTs conducted by district surveillance teams.
2. **Enhanced community-based RACD:** RACD conducted by community-based VMWs using both HS-RDTs and conventional RDTs within villages and among forest workers.

The primary outcome measures to assess effectiveness include *P. falciparum* and *P. vivax* confirmed case incidence over the study period; PCR-based *P. falciparum* and *P. vivax* prevalence at endline; and HS-RDT test positivity rate in village and forest worker RACD. Secondary outcomes measures will examine the operational feasibility, safety, and acceptability of VMW-led reactive approaches and G6PD testing, referral to district or provincial-level facilities, safety and treatment adherence for *P. vivax* cases. The trial will be implemented between June 2019 and December 2020 in Lao PDR. The primary evaluation will be conducted following an end-line cross-sectional survey in November/December 2020.

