3.4. Study evaluation methods

3.4.1. Overview of evaluation activities by study objectives, outcomes, and data collection activities

Table 4. Overview of evaluation activities

Study activity	Research objective	Primary outcome measures	Data collection activity
Activity 1: Impact evaluation of enhanced RACD	1. Evaluate the relative effectiveness of enhanced community-based RACD using HS-	Total confirmed outpatient (OPD) P. falciparum and P. vivax malaria case incidence among all ages by health facility catchment	Routine malaria data from all reporting VMWs, health centers and district hospitals

	RDTs in villages and forest-based HRPs, compared to control	P. falciparum and P. vivax prevalence in all individuals	Cross-sectional parasite survey November-December 2020	
		HS-RDT and RDT test positivity rate	HS-RDT and RDT positivity data from RACD intervention data	
Activity 2: Assessment of the feasibility and acceptability of community-based RACD	1. Assess the operational feasibility of community-based RACD	Population coverage of RACD and interventions	RACD intervention data	
		Proportion of VMWs who rate conducting the RACD interventions as very easy, somewhat easy, somewhat difficult, and very difficult, and changes in proportions over time	Entrance, mid-intervention, and exit competency checklists with VMWs; focus group discussion and interviews with VMWs at end-line	
		Costs of RACD as unit and total costs; cost-effectiveness will be assessed as an incremental cost effectiveness ratio (ICER)	Program data on costs combined with estimates of program effectiveness	
	2. Assess the acceptability of community-based RACD	Proportion of targeted individuals refusing RACD intervention	RACD intervention data	
		Proportion of survey respondents who strongly disagree, disagree, are ambivalent, agree and strongly agree on the importance and acceptability of community-based RACD	Cross-sectional survey and qualitative studies at endline with villagers, forest workers, VMWs and other health sector staff	

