3.4.2.3. Primary outcome measures

1. Confirmed *P. falciparum* and *P. vivax* malaria parasite incidence: defined as the number of OPD malaria confirmed and suspected cases per person per year for each HCCA, as ascertained from the health facility registers, utilizing administrative catchment population size estimates for the exposure denominator.
2. PCR-based *P. falciparum* and *P. vivax* parasite prevalence in sampled HCCAs: defined as the proportion of individuals ≥ 18 months old with *P. falciparum* or *P. vivax* infection (detected by PCR) out of all individuals ≥ 18 months tested within the endline survey (2020).
3. HS-RDT/RDT -based test positivity rate in village and forest-based reactive case detection: defined as the proportion of all individuals tested by HS-RDT/RDT in response to an index cases, with a positive HS-RDT/RDT, among the population older than 18 months.

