3.4.2.4. Sample size

3.4.2.4.1. Confirmed *P. falciparum* and *P. vivax* malaria parasite incidence

Assuming an average baseline transmission of 2.5 per 1000 population per year (all species, from 2017 health system data across study sites and a 50% reduction), an average population of 4000 per health facility catchment, and coefficient of variation of 0.6 (based upon 2017 health system data), in order to detect a 50% reduction in cumulative infection incidence (as measured by routine health system surveillance data over an 18-month period) in a random effects Poisson or negative binomial model, a minimum of 16 randomization units will be required in each study arm. A total of 32 health facility catchment areas will be included in Lao PDR, with 16 allocated each to enhanced RACD and control.

Only health facility catchment areas with at least 3 malaria cases in the past year will be considered for inclusion.

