3.4.2.6. Data management and analysis

Data will be collected via ODK-based tablet application with internal range checks or paper-based with subsequent double-entry, and will be stored in Microsoft Excel or Access. The number of malaria cases, based on RDT and PCR results, will be mapped by village or sub-village and compared between surveys.

Primary outcomes

Outcome 1: Community-level confirmed *P. falciparum* and *P. vivax* malaria parasite incidence

Data pertaining to this outcome will be analyzed on an intention-to-treat basis at the level of health facility catchment area (randomization unit). Cumulative counts of confirmed malaria cases from the health facility registers over the study period and the previous year will be analyzed in a Poisson or

negative binomial regression model with random intercepts at the health center catchment level and an offset for the estimated population size of the catchment area (from administrative data). The models will include a fixed effect for each study arm and a fixed effect for time period (pre- and post-intervention start). The interaction between these two terms will be the primary effect measure (also known as the difference-in-differences estimator). Pre/post-intervention will be determined as all time periods before the start date of the intervention in the areas considered as being pre-intervention and all time periods after (and including the start date of the intervention in the area considered as being post-treatment).

Outcome 2: Community-level PCR-based *P. falciparum* and *P. vivax* parasite prevalence in sampled villages

The effectiveness of the interventions will be assessed as *P. falciparum* and *P. vivax* prevalence via PCR at end-line (post only) using generalized linear mixed effects models with separate random intercepts to allow for clustering within health center catchments. The binomial distribution will be used to analyze prevalence outcomes (logistic regression). All main analyses will be analyzed as intention-to-treat, and all survey clusters will be analyzed within the intervention group assigned at randomization, regardless of adherence. The primary effect estimate will be evaluated using the fixed effects for RACD. Secondary analyses will include adjustment for age, sex, and other potential confounders, and a per-protocol analysis of the primary effect estimate.

Outcome 3: HS-RDT and RDT-based test positivity rate in village-based and forest-based samples

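### Primary Outcome 1 (malaria case incidence) is defined inconsistently: confirmed, or confirmed plus suspected, cases; facility registers or all reporting units; and no explicit rule on infections found by RACD

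*Protocol*

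**What the plan says.** Four parts of the protocol describe Outcome 1.

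- **Definition (3.4.2.3).** Under an item headed as confirmed incidence, the outcome is the "number of OPD malaria confirmed and suspected cases per person per year for each HCCA, as ascertained from the health facility registers".
- **Analysis (3.4.2.6).** "Cumulative counts of confirmed malaria cases from the health facility registers over the study period and the previous year will be analyzed". The model is a Poisson or negative binomial regression, and the effect measure is the interaction of arm with period (difference-in-differences).
- **Overview table (3.4.1, Activity 1).** The outcome is confirmed outpatient cases by catchment. The data source is "Routine malaria data from all reporting VMWs, health centers and district hospitals".
- **Data collection (3.4.2.5.1).** "The confirmed parasite incidence from all reporting units (including HCs, district hospitals, VMWs with RDTs, and PPM sites) will be captured throughout the study".

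Other sections bear on the point:

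- Section 2.5 describes control care as "passive case management provided through community-based VMWs and existing health facilities", so VMWs are a normal point of passive diagnosis.
- Section 3.4.2.4.1 sizes the trial on incidence "as measured by routine health system surveillance data over an 18-month period".
- RACD positivity is a separate primary outcome with its own data source (3.4.1, 3.4.2.3, 3.4.2.5.3).

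**The concern.** Three questions about one primary endpoint get different answers, or none.

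**Which cases?** Section 3.3 (Index case capture) uses *suspected* for people who attend and are then tested. Counting them would make the outcome partly a measure of attendance.

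**Which records?** Two analysts following different sections could build different primary datasets. One would hold VMW and private-sector (PPM) diagnoses and the other might not.

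**Are RACD finds in or out?** In the intervention arm the VMWs who run RACD are also a reporting unit under 3.4.1 and 3.4.2.5.1. Under the facility-register reading a narrower route remains: *P. vivax* positives, including asymptomatic ones, are sent by letter to a facility (3.3.1, Case Management and Follow-up) and could be registered there. RACD is more intensive in the intervention arm (forest workers added, HS-RDT added) than in control (villages, conventional RDTs, some areas only). Any finds that were counted would mix extra detection with the effect on transmission.

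**Working it through.** **1. The texts side by side**

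| Protocol section | Cases | Source |
|---|---|---|
| 3.4.2.3 definition | confirmed and suspected (heading: confirmed) | facility registers |
| 3.4.2.6 analysis | confirmed | facility registers |
| 3.4.1 table | confirmed outpatient | VMWs, health centers, district hospitals |
| 3.4.2.5.1 collection | confirmed | all reporting units, including VMWs and PPM sites |

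The case definition conflicts in one place only, the definition itself. The source splits two against two. No section says that VMW cases are copied into facility registers. The protocol gives no count of suspected cases and no VMW share of diagnoses, so the size of these two conflicts cannot be computed.

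**2. How far RACD finds could move the ratio, if counted**

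Inputs:

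- Tests per index case (3.4.2.4.3): 5 households × 4 people + 4 forest workers = 24. This reproduces the plan's total: 720 × 24 = 17,280.
- Control tests per case where RACD operates: villagers only, 5 × 4 = 20, with the same yield (assumption).
- True ratio: 0.50, the planned effect (3.4.2.4.1).
- RACD positivity *p*: 0.2% is the only RACD yield in the document (section 2, by PCR, from another country). 0.5% and 1% are assumptions.
- Control RACD coverage *c*: 1, 0.5 or 0 (assumptions). Sections 2.5 and 3.4.2.2 (Table 5) both describe some control RACD, so *c* = 0 is an upper bound.

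If no RACD-found person would have presented anyway:

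observed ratio = 0.50 × (1 + 24*p*) / (1 + 20*pc*)

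| *p* | *c* = 1 | *c* = 0.5 | *c* = 0 |
|---|---|---|---|
| 0.2% | 0.504 | 0.514 | 0.524 |
| 0.5% | 0.509 | 0.533 | 0.560 |
| 1% | 0.517 | 0.564 | 0.620 |

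For example, at 1% and *c* = 0: 0.50 × 1.24 = 0.620.

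If only *P. vivax* referrals enter, the vivax share from Table 1 is 2.79/6.77 = 0.412. With *c* = 0 and all attending, the ratio is 0.50 × (1 + 24 × 0.412 × *p*) = 0.510 at 0.2% and 0.549 at 1%.

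Section 2.1 says household RACD was not yet operating in southern Lao PDR. The baseline year therefore holds no matching excess, and the difference-in-differences term would not remove it.

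**3. The opposite error of a passive-only count**

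Let *b* be the share of RACD-found people who would have presented anyway.

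- Passive-only ratio = 0.50 × (1 + 20*pbc*) / (1 + 24*pb*)
- All-detected ratio = passive-only ratio × (1 + 24*p*) / (1 + 20*pc*)

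With *b* = 0.5 (assumption):

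| *p* | Count | *c* = 1 | *c* = 0.5 | *c* = 0 |
|---|---|---|---|---|
| 0.2% | passive-only | 0.498 | 0.493 | 0.488 |
| 0.2% | all-detected | 0.502 | 0.507 | 0.512 |
| 1% | passive-only | 0.491 | 0.469 | 0.446 |
| 1% | all-detected | 0.507 | 0.528 | 0.554 |

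In these scenarios the two counts bracket the true 0.50.

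**The case against.** **RACD finds are already excluded by the wording.** Both the definition and the overview table say outpatient, and a household or forest-site test is not an outpatient visit. The sample size rests on routine surveillance data. RACD has its own outcome, and *P. vivax* referrals have their own registry (3.4.2.5.3) and facility G6PD register form (appendix list). This largely stands. A reader might infer that the trial will count RACD finds and is biased toward no effect; the document does not support that. What remains is that outpatient is never tied to detection mode, and VMW data enter without separating passive from RACD diagnoses.

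**Inclusion rules belong in the analysis plan.** This is fair for the RACD rule taken alone, and that plan was not available. It does not answer the contradictions on case type and source, which lie within the protocol.

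**The sources may be compatible.** Section 3.4.2.5.1 itself mentions facility registers, so all units might be captured and then compiled there. This is possible but not stated. A reader might also take the summary's "Cumulative incidence over the study period at the health facility level" as a further source statement; it more naturally names the level of aggregation.

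**The shift is small.** It is, at 0.2%. Larger values need assumed positivity, and 0.62 also needs no control RACD. Section 3.2 excludes people seen in an RACD event within the past 30 days, so 24 tests for every index case is on the high side. On the other side, section 2 expects RACD aimed at high-risk groups to find more infections than neighborhood RACD.

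**Sample size.** A reader might infer that the trial is underpowered. Nothing here supports that, and the 16 clusters per arm are not in question.

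**Conclusion.** The inconsistency is real and concerns a primary endpoint. As written, section 3.4.2.3 counts suspected cases against its own heading and three other sections, and the four descriptions do not share one source. Neither finding needs a numerical assumption, and neither can be sized from the document.

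The RACD question is secondary. The evident intent is a count of passively presenting cases, but it is not secured by a rule. If RACD finds were counted, the ratio would tend toward 1, provided the intervention arm records more RACD finds per passive case than control; equal yield per case would leave it unchanged. From a true 0.50 the result is 0.50 to 0.52 at 0.2% positivity. At an assumed 1% it is 0.52 to 0.56 with full to half control coverage, and 0.62 only as an upper bound. The actual size is unknown. Endline PCR prevalence, also primary, is unaffected. This should be fixed, but it does not undermine the design.

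**What to change.** 1. Delete *and suspected* from the definition in 3.4.2.3.
2. Use one source list, all reporting units including VMWs, in 3.4.1, 3.4.2.3, 3.4.2.5.1 and 3.4.2.6.
3. State that the primary count in both arms is parasitologically confirmed cases who presented themselves to a reporting unit.
4. Report RACD-found infections separately. In the intervention arm, identify them through the existing unique codes, referral letters and *P. vivax* registry (3.4.2.5.3). In the control arm, add a simple mark for cases found by district RACD teams, since nothing described now identifies them.
5. Pre-specify an all-detected count as a sensitivity analysis.

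The cost is wording in four sections and one mark in the case records. Control-arm marking depends on the district teams, and slightly fewer cases are counted. A passive-only count can lean toward benefit if some RACD-found people would have presented anyway. With half of them doing so and no control RACD, 0.50 reads as 0.49 at 0.2% positivity and 0.45 at 1%. The two counts should therefore be reported and read together.

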3.4.2.5.2. Cross-sectional surveys

An endline survey will be conducted in November/December 2020 to obtain an unbiased estimate of *P. falciparum* and *P. vivax* malaria parasite prevalence in each study arm, as well as assess intervention coverage, treatment seeking, and mobility and forest going activities. The endline survey will include testing with HS-RDTs/RDTs and collection of DBS for qPCR-based testing.

Sampling frame and sampling strategy

Within each of the HCCAs selected for study inclusion, survey staff will work with village authorities to update household ledgers, and then all households will be enumerated and a GPS point captured. All households will be given a study ID card and household sticker with a unique barcode, which will be used throughout the study to identify repeat visits at each household, as well as for individuals to present at health facilities if they report for care.

In order to reduce potential contamination due to proximity to intervention areas (for the control arm), households within 2 km of a neighboring study village will be removed from the sampling frame. Households will be selected via simple random sampling from the remaining HH lists.

Questionnaires and human specimen collection

During the endline survey, selected households will be visited and the head of household interviewed by a study staff member using a tablet or paper form. To capture any household members not present at time of survey, study staff will plan for an overnight stay whenever feasible to schedule visits for early morning or late evening, but will have a maximum of four visits to each HH. The survey questionnaire used for interviewing will be developed in English with input from local health staff. This

will then be translated to Lao, and back-translated by a fluent bilingual health expert prior to field testing.

The survey questionnaire will capture household-level demographics, and assess potential risk factors for malaria infection. Information collected will include age, gender, pregnancy, nationality, ethnicity, occupation, socioeconomic status, travel history, history of malaria, treatment seeking for fever in the past two weeks, individual and household use of vector control measures, housing structure type, proximity to forest and forest-fringe, and frequency of overnight sleeping in forest or forest-fringe areas.

At the endline survey, all household members (residents and temporary visitors) aged 18 months and older will be invited to participate in an RDT and blood collection component. Informed consent will be obtained from all participants, including parental consent for any participant younger than 18 years of age. After consenting, the study team will capture axillary temperature, and test each individual using a standard combination RDT and an HS-RDT (SD Bioline Malaria Ag P.f High Sensitive Cat# 05FK140), and Hemocue kit, followed by collection of four DBS on filter paper.

If found positive by RDT or HS-RDT, treatment will be administered as in Section 3.1.1. Testing results from the collected DBSs will not be provided to the participants.

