3.4.2.2. Randomization

A total of 32 health center catchment areas (HCCAs) in Laos will be selected for inclusion based upon incidence per 1000 population between October 2017 and September 2018. HCCAs with higher incidence will be prioritized to improve power; where possible, directly neighboring HCCAs will not both be included to reduce contamination. Restricted randomization of the HCCAs into either RACD or control arms will be conducted, whereby sets of randomizations (with 16 HCCAs in each arm) will be generated that achieve balance across arms on incidence per 1,000 over the prior year, population size, and amount of forest cover. From these sets of potential randomizations, a single randomization will be randomly selected to assign 16 HCCAs each to the RACD or control group. Restricted randomization in this way will ensure balance across intervention and control groups on potential confounding factors. The 'sample' command in Stata v14 (StataCorp, College Station, TX) will be used to implement randomization.

Table 5. Study arms

Study arm	Description	Lao PDR
RACD	Reactive case detection led by VMWs in response to cases in study area HCCA, with follow up testing with HS-RDTs/RDTs in both villages and forest workers; referrals for qualitative G6PD testing for P. vivax cases and 14-day PQ for G6PD non-deficient	16
Control	Standard of care including case management through health facilities and malaria posts/VMWs; village-based RACD conducted by district staff in some areas	16

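### The 2 km exclusion from the endline sampling frame does not fix which arms or which villages it covers; applied to control households only, it would make entry to the prevalence comparison depend on arm

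*Protocol*

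**What the plan says.** Section 3.4.2.5.2 sets up the endline survey to estimate, without bias, "malaria parasite prevalence in each study arm, as well as assess intervention coverage". All households in the study catchments are listed and given a GPS point. The exclusion sentence then opens with its reason and trigger, "In order to reduce potential contamination due to proximity to intervention areas (for the control arm), households within 2 km of a neighboring study village", and from the parenthesis to its end, where the action stands, it reads: "for the control arm), households within 2 km of a neighboring study village will be removed from the sampling frame". After that, "Households will be selected via simple random sampling from the remaining HH lists".

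Section 3.4.2.6 assesses "prevalence via PCR at end-line (post only) using generalized linear mixed effects models", with a random intercept per catchment. It follows intention to treat: "all survey clusters will be analyzed within the intervention group assigned at randomization, regardless of adherence". PCR prevalence is one of the primary outcomes in Section 3.4.2.3.

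Section 3.4.2.2 gives a first defence against contamination when catchments are chosen: "where possible, directly neighboring HCCAs will not both be included to reduce contamination". It also restricts the randomisation to balance prior incidence, population size and forest cover over whole catchments.

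**The concern.** The exclusion sentence leaves two things open, and no other section of the protocol settles them.

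1. **Which arm loses households.** The only arm named is control, and closeness to intervention areas threatens control households in particular. Survey staff would most naturally trim the control catchments only. A household's eligibility would then depend on the arm it was assigned to.
2. **Which villages trigger removal.** The term used is not defined and not limited to villages of the other arm, although the stated purpose concerns intervention areas only.

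Randomisation balances whole catchments. Trimming one arm's frame afterwards means that the balance no longer covers the households compared. Analysing clusters by assigned arm does not repair selection within clusters, and an endline-only model has no baseline prevalence with which to correct a difference in frames.

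**Working it through.** **The plan's own figure.** Section 3.4.2.4.2 gives 16 catchments per arm, control prevalence p0 = 0.025, a 50% reduction (p1 = 0.0125), coefficient of variation k = 0.5 and m = 400 per catchment. Two-sided 5% and 80% power are my assumptions, as that section states neither. The unmatched cluster formula of Hayes and Bennett is

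c = 1 + (1.96 + 0.84)² × V, with V = [p0(1-p0)/m + p1(1-p1)/m + k²(p0² + p1²)] / (p0-p1)².

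- V = (0.0000609 + 0.0000309 + 0.0001953) / 0.00015625 = 1.8375.
- c = 1 + 14.42 = 15.4, which rounds up to 16.
- Power at 16 per arm = Φ(√(15/1.8375) - 1.96) = 81.5%.
- Survey total: 32 × 400 × 1.1 = 14,080, as stated.

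The sample size reproduces. The point is about the sampling frame, not an arithmetic error.

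**Control-only reading.** Let f be the share of households within the buffer and r their prevalence relative to interior households, both taken as equal across arms before any effect. Let p be interior prevalence.

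- Intervention frame (nothing removed): (1-f)p + f·r·p.
- Control frame (interior only): p.
- Ratio under no effect: (1-f) + f·r.

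| f | r | Ratio under no effect |
|---|---|---|
| any | 1 | 1.00 |
| 0.2 | 0.67 | 0.8 + 0.134 = 0.93 |
| 0.2 | 1.5 | 0.8 + 0.30 = 1.10 |

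If the true ratio is 0.5, the last row gives an observed ratio of 0.5 × 1.10 = 0.55. Interior control prevalence is then 0.025/1.10 = 0.0227, V = 2.434, and power is Φ(√(15/2.434) - 1.96), about 70%. At r = 0.67 the observed ratio is 0.5 × 0.934 = 0.467, which overstates the effect.

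**Both-arms reading, any study village.** Table 1 lists 300 villages in 32 catchments: 300/32 = 9.4 per catchment. Taken literally, villages of the same catchment, or of another catchment in the same arm, would trigger removal. They share the household's allocation, so removal serves no contamination purpose. The protocol gives no distances, so the share lost cannot be computed.

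**Can the buffer be triggered at all?** Adjacent catchments are avoided only where possible, and Table 1 places six study facilities in one district (Toumlan). So it can, to an unknown extent.

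**The case against.** The strongest reply is grammatical. The mention of the control arm sits in the purpose clause and says whom contamination threatens; the removal clause applies to no named arm. This stands: the text does not establish control-only removal, and a both-arms rule is a possible reading. It does not rescue the sentence, because the triggering village is still not tied to the other arm.

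Second, counting villages of the same catchment is strained. The stated purpose and the use of the neighbouring idea in Section 3.4.2.2 both point to other catchments. That is fair as to intent, but the rule as worded does not say so.

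Third, the bias is conditional. It needs the control-only reading, a removed share that matters, and r different from 1. The protocol shows none of these. Avoiding adjacent catchments should keep f small. Section 3.4.2.5.2 collects forest proximity and forest overnight stays, and Section 3.4.2.6 plans secondary adjustment for potential confounders. These points limit the likely size, but they do not protect the primary estimate. That location matters is plausible: Section 2 reports higher infection risk among people who had worked in or near the forest fringe. It is not shown for the households in the buffer.

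Fourth, the remedy is partly a choice. Keeping the full frame in both arms, with the buffer as a sensitivity analysis, would also be symmetric. That is true; the essential requirement is that the rule does not differ by arm.

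**Conclusion.** The exclusion rule is badly fixed and should be reworded. It does not say which arms it covers, and the villages that trigger it do not match its stated purpose. Applied to control households only, it would work against the survey's aim of an unbiased estimate in each arm, for a primary outcome. The illustrative bias is a ratio of 0.93 to 1.10 under no effect at f = 0.2 and r from 0.67 to 1.5, and none at r = 1. Both f and r are assumptions, and the direction is unknown.

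A reader might infer three stronger things that the protocol does not support:

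- **That the arms' samples certainly come from different populations.** This holds only on one reading of the sentence.
- **That the bias is large.** For example, f = 0.4 and r = 2 give 0.6 + 0.8 = 1.40, but nothing in the protocol supports such values.
- **That no baseline survey exists.** Sections 5.2 and 5.4 mention one. What can be said is that the prevalence analysis uses no baseline.

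**What to change.** Replace the exclusion sentence with: *In both arms, households within 2 km of a study village allocated to the opposite arm are removed from the sampling frame.* Report the number removed per arm. Household GPS points are already planned and villages are to be mapped (Section 3.4.2.5.1), so no new data are needed. If the rule is applied before sampling, the planned 14,080 does not change.

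If sampling has already been done with control-only removal, apply the same 2 km opposite-arm restriction to the sampled intervention households in the prevalence analysis. This makes the frames comparable only if the control removals were themselves triggered by opposite-arm villages, so the rule actually used should be stated.

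The cost is one sentence in the protocol and the sampling procedure, and an intervention-arm frame that no longer covers border households. The after-the-fact restriction also loses sampled people. Under the formula above, 16 catchments per arm need about 356 per catchment for 80% power when both arms are that size, so the slack is 400 - 356 = 44, or 11%.
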